This protocol has been evaluated in a large phase III trial including patients with metastatic colorectal cancer¹². Please see appendices I-IV for details of the chemotherapy regimens.

5. Aims

The **primary aim** of the New EPOC trial is to determine whether the addition of Cetuximab to Oxaliplatin plus modified de Gramont or Irinotecan plus modified de Gramont combination chemotherapy results in improved progression free survival when compared with combination chemotherapy alone in patients who do not possess a kRAS mutant genotype confirmed by laboratory analysis.

Secondary aims

1. To evaluate overall survival.
2. To evaluate quality of life.
3. To compare the experimental arm in terms of cost effectiveness in a UK treatment setting
4. To determine whether the addition of Cetuximab to combination chemotherapy as above results in improved progression free survival when compared with combination chemotherapy alone in patients who possess the kRAS-wt genotype confirmed by laboratory analysis

Translational research aims

1. To assess the difference in progression free survival with chemotherapy plus Cetuximab for all patients irrespective of EGFR detectability in tumour tissue on IHC; for patients with detectable EGFR and for those with undetectable EGFR.
2. To determine, from DNA extracted from peripheral blood, the impact of individual variance in DNA repair capacity on tumour response, progression free survival and grade 3/4 toxicities.
3. To determine, from DNA extracted from peripheral blood, whether variance in the enzymes involved in the metabolism, transport and cellular targets of the drugs used affects tumour response, progression free survival and grade 3/4 toxicities.
4. To determine the effect of Cetuximab on the expression profile of hepatic metastases.

6. Outcome measures

Primary: progression-free survival.

Secondary: pre-operative response, pathological resection status, peri-operative safety findings, overall survival, EQ-5D, EORTC QLQ-C30, EORTC QLQ-LMC21, measures for cost effectiveness.

Definitions

Progression-free survival (PFS) is defined as the time from randomisation to first recurrence/disease progression or death, whichever occurs first. Patients not experiencing recurrence/progression/death will be censored at the date of the last follow-up examination. PFS will be assessed as follows:

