In patients with resected metastases (R0 or R1 or R2), PFS will be considered to be the time from randomisation to the first of the following events:

- Recurrence/disease progression after surgery
- Death

In patients with unresected metastases, PFS will be considered as the time from randomisation to the first of the following events:

- Disease progression (whenever it occurs, before or after the planned surgery date)
- Death

Overall survival is defined as the time interval between the date of randomisation and the date of death. Patients who are still alive when last traced will be censored at the date of last follow-up.

Pre-operative response: evaluation of the activity of study treatment on hepatic metastases will be done according to the RECIST criteria (see Appendix V), after the end of the pre-operative treatment period by abdominopelvic computed tomography (CT) scan or magnetic resonance imaging (MRI) ideally within 1 week but not longer than 2 weeks. As patients will undergo surgery

within 2 to 4 weeks of CT scanning at the end of the pre-operative period, the 4 week confirmation does not apply for patients who achieve their first response at this time point.

A pre-operative safety finding will be if >6 weeks delay of surgery due to study treatment-related toxicity, with the delay being measured between the end of pre-operative chemotherapy (last day of last cycle) and surgery.

Pathological resection rate: following surgery, the pathologist will assess the resection as R0, R1 or R2. The rates of R0, R1 and R2 resections will be presented.

Peri-operative safety findings: any of the following events provided they are due to a severe surgery-related complication (i.e. wound infection, intra-abdominal infection, severe sepsis.):

- Prolongation of hospitalisation (discharge >20 days after surgery)
- Re-hospitalisation within 30 days of surgery
- Re-operation under general anaesthesia within 30 days of surgery (excluding secondary surgery after R1 resection)
- Death during surgery or within 30 days of surgery
- Other severe pre- or post-operative complications within 30 days of surgery:
 - Surgery-associated bleeding with replacement ≥ 4 units of erythrocyte concentrates
 - Biliary fistula for more than 10 days with a discharge of >100 mL/day
 - Transient liver failure, defined as a bilirubin level >10 mg/dL lasting >7 days
 - Renal failure requiring dialysis

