 - Respiratory failure with renewed necessary mechanical ventilation or >26 h necessary mechanical ventilation
 - Deep venous thromboembolism
 - Cardiac failure
 - Major impaired wound healing necessitating re-operation, delaying the start of the post-operative study treatment by more than 8 weeks (delay being measured between surgery and start of post-operative study treatment) or prolonging hospitalisation (discharge >20 days after surgery)
- >8 weeks delay of the start of post-operative study treatment due to complications; delay being measured between surgery and start of post-operative study treatment
- Severe pre- or post-operative toxicity of study treatment leading to treatment discontinuation (all drugs discontinued) or death

Note: the occurrence of minor surgery and minor impaired wound healing are not part of the endpoint definition but will be collected on the CRFs for descriptive purposes.

7. Centre and investigator selection

In order to participate in the New EPOC trial, investigators/centres must fulfill a set of basic criteria and witness this by signature of the New EPOC Commitment Form. This form will be sent to centres as soon as they express an interest in the trial. Criteria are:

- Ethical approval to participate in the trial according to their national and, for European centres, European rules and regulations
- Identification of an investigator responsible for the institution's participation in New EPOC who fulfills the legal requirements for investigators in biomedical research of the country in which the institution is situated
- Local infrastructure sufficient to guarantee that the investigations and treatment measures required by the protocol can be performed without undue delay
- Local infrastructure sufficient to guarantee follow-up
- Willingness to allow monitoring (source data verification)
- Willingness to comply with the protocol in all aspects of patient care, specimen handling and data management, as witnessed by signature(s) on the commitment form
- Familiarity with the chemotherapy agents under investigation, and the standard of supportive care required for these patients
- Familiarity with hepatic resection centre for hepatic metastases or part of a network with established links with a centre

The commitment form is signed by the Principal Investigator on behalf of all staff at their centre who will be working on the New EPOC trial.

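### The definition of peri-operative safety findings contradicts its own list: the lead-in admits only infective causes, while most of the named events need not be infective

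*Protocol*

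**What the plan says.** Section 6 (Outcome measures) of the protocol lists the outcome among the secondary measures: "Secondary: pre-operative response, pathological resection status, peri-operative safety findings, overall survival". The definition that follows counts a listed event only "provided they are due to a severe surgery-related complication (i.e. wound infection, intra-abdominal infection, severe sepsis"; the parenthesis says what such a complication is.

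Fourteen items come under that lead-in:

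- **Four general events:** prolonged hospital stay, re-hospitalisation, re-operation, and death during or within 30 days of surgery.
- **Eight complications** under the sub-heading "Other severe pre- or post-operative complications within 30 days of surgery": bleeding ("Surgery-associated bleeding with replacement ≥ 4 units of erythrocyte concentrates"), biliary fistula, transient liver failure, renal failure needing dialysis, respiratory failure, "Deep venous thromboembolism", cardiac failure, and major impaired wound healing.
- **One delay item:** post-operative study treatment starting more than 8 weeks late because of complications.
- **One toxicity item:** severe study-treatment toxicity that leads to stopping all drugs or to death.

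A closing note takes only minor surgery and minor impaired wound healing out of the definition.

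**The concern.** The lead-in sets a causal condition for every item below it and defines that condition by three infective states, with nothing such as *etc.* to leave the set open. Most of the named complications are surgical events in their own right that can arise without infection, and the toxicity item has a drug cause. A definition that names an event and then excludes it unless infection produced it cannot be applied consistently.

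This is the composite in section 6 for surgical harm; the separate pre-operative safety finding is a single item on delay of surgery. Under the literal rule the composite misses non-infective events. Under a looser rule the count depends on who does the classifying, and section 2 describes the trial as open-label, so an assessor may know the arm. Section 12.a adds a practical consequence: events that are secondary outcome measures are not handled as SAEs, so whether a non-infective bleed is an outcome event also decides how it is reported.

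**Working it through.** The protocol gives no expected complication rate and no infective share, so there is no figure to reproduce. The check sets the lead-in against each part of the list.

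**1. Scope of the proviso.** It stands before the first bullet and refers to all the events that follow. It therefore governs 4 + 8 + 1 + 1 = 14 items.

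**2. Meaning of the parenthesis.** Elsewhere the protocol uses the two abbreviations in their proper senses. In the exclusion criteria of section 8, *e.g.* introduces examples of unfitness for chemotherapy, and *i.e.* fixes what counts as a very recent MI. A reader has reason to take *i.e.* in section 6 as a definition too.

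**3. Literal result, item by item.**

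| Items | Can the item meet an infective, surgery-related cause? |
|---|---|
| Stay, re-hospitalisation, re-operation, 30-day death (4) | Only when infection is the cause; otherwise not counted |
| Bleeding, biliary fistula, liver, renal, respiratory and cardiac failure, thromboembolism (7) | Need not be infective; not counted unless infection caused them |
| Major impaired wound healing (1) | Fits readily where the wound is infected |
| Late start of post-operative treatment (1) | Carries its own, wider causal clause (complications), which the lead-in then narrows |
| Study-treatment toxicity (1) | Hardly ever; the cause is the drug |

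So 7 of the 8 sub-listed complications, plus the toxicity item, conflict with the lead-in. That is 8 of 14 items. A 30-day death from haemorrhage would also fall outside the count.

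**4. Signs of what was meant.** The sub-heading presents its items as other severe complications, on a par with those in the parenthesis. The re-operation item expressly excludes secondary surgery after an R1 resection, which would be redundant if only infection-driven re-operations counted. The toxicity item would be almost empty under the literal rule. The closing note excludes only minor events. All four point to non-infective events being intended to count.

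**5. Size.** If every site applied the literal rule, the recorded rate would be the true rate multiplied by the proportion of true events due to one of the three infective conditions. The protocol supplies neither factor, so no number can be put on the shortfall.

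**6. Correction elsewhere.** No other part of the protocol widens the condition or restates the definition.

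**The case against.** The strongest reply is that this is a drafting slip with an obvious intent. The signs in step 4 support that, and sites may already be classifying sensibly. A reader might infer from the wording that the sponsor meant to count infective events only. The documents do not support that inference.

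A reader might also infer that bleeding, bile leak or liver failure would be hidden from view. That goes too far as well. Section 9.c asks for blood loss and extent of resection to be noted, and for serious complications to be reported within a month of the operation so that the arms can be compared, with no limit to infection. Section 11.f has surgical data returned on a surgery form, and section 11.g has all deaths reported on the Death CRF. A death at operation still counts in PFS and overall survival. Nor does the SAE carve-out in section 12.a lose a non-infective bleed under the literal reading: if the bleed is not an outcome event, the carve-out does not apply to it.

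Finally, this is one of several secondary outcomes, and section 18 attaches no test, power or decision rule to it.

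These points limit the consequence, but the stated rule still gives a wrong count if followed. The detail is not one that was merely left to a statistical analysis plan, because the protocol fixes a definition and that definition contradicts itself. An obvious intent does not tell two assessors how to code the same thromboembolism while the text says otherwise.

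**Conclusion.** The point holds as an internal contradiction in the definition of a secondary outcome. Followed literally, the rule counts 7 of the 8 named complications only when infection caused them and all but removes the toxicity item, so the composite is under-counted. Followed loosely, it leaves classification open to inconsistency in an open-label trial.

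The size of the effect cannot be derived from the protocol. Any statement that the rate falls by a given fraction would rest on an assumed event rate, an assumed infective share, and literal application at every site. No between-arm bias is demonstrated: a literal rule would lower the count in both arms, and whether it would do so equally is unknown.

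The conclusion rests on reading *i.e.* as definitional and the proviso as governing the whole list, which is what the text says. It does not rest on any view that the sponsor intended to drop non-infective events. The correction is worth making because the wording fixes an outcome rule and is cheap to change.

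**What to change.** Amend the definition in section 6 as follows:

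- Change *i.e.* to *e.g.*, or otherwise open the parenthesis to any severe surgery-related complication.
- Apply the causal proviso only to prolonged stay, re-hospitalisation and re-operation.
- State that death during or within 30 days of surgery, each named complication and the study-treatment toxicity item count in their own right. The late-start item already carries its own causal clause and needs no second one.
- Apply the rule to events already recorded without reference to results by arm, and document how they are reclassified.

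The cost is a wording change and some reclassification. Reported complication rates may rise, though they may not if sites have been reading the list broadly. The surgery form is not shown, so it is plausible but unconfirmed that reclassification can be done from data already held. Treatment, sample size and the primary analysis are untouched.

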- The ambulatory technique for OxMdG and IrMdG is described in AAppendix III. These regimens may also be given on an inpatient basis, but investigators are urged to use outpatient ambulatory treatment whenever possible.

9.b Treatment duration and breaks

- **Arm A (Control, OxMdG / IrMdG):** These patients will receive 12 weeks of pre-operative and 12 weeks of post-operative chemotherapy dependent on cumulative toxicity, post-surgical performance status or because of patient choice to stop chemotherapy. Patients in this arm should continue on treatment with no more than a three week interval off treatment for any reason although the post surgical interval can be 6 weeks. *The cumulative toxicity that is most likely to occur is the neuropathy associated with Oxaliplatin, which increases in incidence from about 12 weeks duration of therapy. If this occurs, patients may continue on the fluorouracil component of the regimen with dose increment as indicated in Appendix I.* If the neuropathy resolves to < grade 1 the Oxaliplatin may be reintroduced cautiously at the investigator's discretion.
- **Arm B: OxMdG / IrMdG plus Cetuximab:** These patients will receive chemotherapy as Arm A above plus Cetuximab. Patients in this arm should continue on treatment with no more than a three week interval off treatment for any reason although the post surgical interval can be 6 weeks. Cetuximab will be continued if chemotherapy is stopped because of toxicity or patient choice, but should be discontinued on recurrence or unacceptable Cetuximab toxicity. Full details of Cetuximab administration and dose reduction and delays are given in Appendix I.

9.c Surgery

The liver resection is carried out **at the earliest 4 weeks** after the last administration of chemotherapy and Cetuximab, and within 2 to 6 weeks of CT scanning at the end of the pre-operative period. Patients who progress during the first 12 weeks of chemotherapy and who are still operable should be considered for surgery. However these patients are unlikely to be salvaged with surgery and consideration should be given to second-line chemotherapy. In addition, the patient must have completely recovered from side effects, the general condition according to WHO grade must be ≤ 1 and liver function must be adequate for liver surgery.

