The Investigator should **assess** each SAE for the likelihood that it is a response to the investigational medicines. The SAE will also be evaluated by an allocated Clinical Reviewer at the request of UoSCTU for seriousness, expectedness and causality. Investigator reports of suspected SARs will be reviewed immediately and those that are SUSARs identified and reported to regulatory authorities. The causality assessment given by the Investigator cannot be overruled and in the case of disagreement, both opinions will be provided to the authorities with the report.

All SUSARs reported to UoSCTU will be forwarded to Merck kGaA.

13. Protocol deviations and withdrawal of patients

All protocol deviations should be reported to University of Southampton Clinical Trials Unit at the earliest opportunity.

In consenting to the trial, patients are consenting to trial treatment, trial follow-up and data collection. If a patient wishes to withdraw from trial treatment, centres should nevertheless explain the importance of remaining on trial follow-up, or failing this of allowing routine follow-up data to be used for trial purposes. If the patient explicitly states their wish not to contribute further data to the study, UoSCTU should be informed in writing and an End of Study form completed.

13.a Withdrawal from trial intervention

A patient may withdraw, or be withdrawn, from trial treatment for the following reasons:

- Progression whilst on therapy
- Unacceptable toxicity
- Intercurrent illness which prevents further treatment
- Withdrawal of consent for treatment by patient
- Any alterations in the patient's condition which justifies the discontinuation of treatment in the investigator's opinion.

The patient should however remain in the trial for the purposes of follow-up and data analysis.

14. Trial closure

We plan to recruit 288 patients which we anticipate we will reach at the end of December 2012. We will then follow-up all patients for 5 years after the trial closes to patient entry.

For the purposes of regulatory requirements the end of the trial will be the final date on which data was (or is expected to be) collected'.

15. Quality of life

15.a QoL timing

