Grade 3 or Grade 4 Grade 3: Symptomatic bronchospasm, with or without urticaria; parenteral medication(s) indicated; allergy-related oedema/angioedema; hypotension Grade 4: Anaphylaxis	Stop Cetuximab infusion immediately and disconnect infusion tubing from the patient. Administer adrenaline, bronchodilators, antihistamines, glucocorticoids, intravenous fluids, vasopressor agents, oxygen etc., as medically indicated. Patients have to be withdrawn immediately from treatment and must not receive any further Cetuximab treatment.

- Once the infusion rate has been slowed for an allergic reaction, it should remain at the slower rate for all subsequent infusions.
- If the patient has a second allergic/hypersensitivity reaction on the slower infusion rate, the infusion should be stopped and no further Cetuximab administered.

- If a patient receives a grade 3 or 4 allergic/hypersensitivity reaction at any time, Cetuximab must be discontinued, but remaining chemotherapy treatment should be continued as normal.
- If there is any doubt whether a reaction is an allergic/hypersensitivity reaction of Grades 1-4, the trial principal co-investigator [name] should be contacted immediately to discuss and grade the reaction.

Skin toxicity - Cetuximab

[figure not shown]
- The acneiform skin rash associated with Cetuximab occurs in over 70% of patients. About 12% have grade ≥ 3 reactions. On longer-term therapy, paronychia occurs in about 10% of patients and can be painful.
- Discussion with a local dermatologist prior to study initiation would be helpful to agree local plans of management and mechanisms for rapid referral in case of severe skin toxicity.
- The occurrence of the rash has been correlated with an increased likelihood of response to treatment, though this information needs to be used with caution, as it is not a direct correlation.
- The rash usually occurs on the face, upper chest and back with multiple follicles and pustules. The onset is usually within the first 3 weeks of treatment and many cases improve by 12 weeks on treatment.

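### The peri-operative safety outcome is defined inconsistently: its surgery-related proviso shuts out drug toxicity, and without the proviso its discontinuation test is harder to meet in Arm B

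*Protocol*

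**What the plan says.** Section 6 of the protocol names the outcome among the secondary measures: "Secondary: pre-operative response, pathological resection status, peri-operative safety findings, overall survival". Its definition, under the same heading, counts "any of the following events provided they are due to a severe surgery-related complication", with wound infection, intra-abdominal infection and severe sepsis given as the complications meant. A list of events follows. The last of them is "Severe pre- or post-operative toxicity of study treatment leading to treatment discontinuation (all drugs discontinued) or death". Nothing in that item or in the note after it exempts it from the opening condition.

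Section 9.b sets what happens in Arm B when treatment is stopped in part: "Cetuximab will be continued if chemotherapy is stopped because of toxicity or patient choice, but should be discontinued on recurrence or unacceptable Cetuximab toxicity". For OxMdG plus cetuximab, Appendix I covers the reverse case after a grade 3 or 4 hypersensitivity reaction: "Cetuximab must be discontinued, but remaining chemotherapy treatment should be continued as normal". For oxaliplatin neuropathy, section 9.b says that "patients may continue on the fluorouracil component of the regimen with dose increment as indicated in Appendix I". It says so for Arm A, and Arm B receives its chemotherapy as Arm A does. Section 13.a allows withdrawal from all trial treatment for unacceptable toxicity, in either arm.

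**The concern.** The definition has two defects, and they belong to alternative readings of the same text.

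First, a proviso about surgical complications governs an item about the toxicity of study drugs. Pre-operative drug toxicity comes before the operation and cannot be due to a complication of it. Post-operative drug toxicity would qualify only where a surgical complication caused it. Whoever classifies events must either apply the proviso and lose almost all toxic discontinuations and toxic deaths, or set the written definition aside.

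Second, once the proviso is set aside, the item requires that every drug be stopped. Arm A patients have only chemotherapy to stop. Arm B patients have chemotherapy and cetuximab, and section 9.b keeps the second going when the first is stopped for toxicity. The same toxic event can therefore be scored in one arm and not in the other.

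At stake is a between-arm comparison of safety around liver resection in an open-label trial whose question is the effect of adding cetuximab. One reading leaves this item almost empty. The other gives it an arm-dependent threshold.

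**Working it through.** The protocol gives no rate, power or sample size for this outcome, so there is no figure of its own to reproduce. The check compares the passages, and then illustrates the size.

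**Reading 1: the proviso applies to the toxicity item.** An event must be both toxicity of study treatment and due to a severe surgery-related complication. Pre-operative toxicity never satisfies both. Post-operative toxicity does so only if a surgical complication caused it. The restriction is the same in both arms, so the loss is of content and not of balance.

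**Reading 2: the proviso does not apply to the toxicity item.** Under sections 6, 9.b and 13.a and Appendix I, cases are scored as follows.

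| Case | Arm A | Arm B |
|---|---|---|
| Oxaliplatin stopped for neuropathy, 5FU continues | not counted | not counted |
| All chemotherapy stopped for severe toxicity, cetuximab (if given) continues as in 9.b | counted | not counted |
| All chemotherapy and cetuximab stopped for toxicity | not applicable | counted |
| Cetuximab alone stopped for toxicity | not applicable | not counted |
| Death from treatment toxicity | counted | counted |

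The second row is where the arms part. The fourth shows that a permanent stop of the experimental drug alone is also missed.

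**Size under reading 2, discontinuation limb only.** Inputs:

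- n = 134 per arm, from the sample size calculation in section 18.
- p = probability that all chemotherapy is stopped for severe toxicity, taken as equal in both arms (assumed; not in the protocol).
- q = share of those Arm B patients who also stop cetuximab (assumed; not in the protocol).

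Expected count in Arm A = n × p. Expected count in Arm B = n × p × q.

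| p | Arm A | Arm B, q = 0.1 | q = 0.3 | q = 0.5 | q = 1 |
|---|---|---|---|---|---|
| 5% | 6.7 | 0.7 | 2.0 | 3.4 | 6.7 |
| 10% | 13.4 | 1.3 | 4.0 | 6.7 | 13.4 |
| 20% | 26.8 | 2.7 | 8.0 | 13.4 | 26.8 |

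For example, at p = 10% and q = 0.3: 134 × 0.10 = 13.4 against 134 × 0.10 × 0.3 = 4.0.

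**Unequal stopping rates.** Let the rates be pA and pB. The recorded ratio of Arm B to Arm A is then q × pB / pA, against a true ratio of pB / pA. The Arm B count is scaled down by q, but the direction of the recorded difference is not fixed. With pA = 10%, pB = 20% and q = 0.5, both arms record 13.4 (134 × 0.10, and 134 × 0.20 × 0.5), which hides a doubling.

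**The case against.** The strongest reply is that this is a drafting fault in one component of one secondary outcome, and that toxicity is seen elsewhere. NCI toxicity scores are taken at every cycle (section 11.e), a surgical delay of more than 6 weeks due to treatment toxicity is a separate finding outside the list (section 6), toxicity is among the quality-of-life endpoints (section 15.b), and deaths are reported on their own form and count in progression-free and overall survival. All of this stands and limits the importance of the point. None of it repairs the definition.

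A reader might go further than the text allows in four ways.

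- *That Arm B largely cannot meet the criterion.* The rule in section 9.b also stops cetuximab for its own unacceptable toxicity, section 13.a allows full withdrawal in either arm, and toxic death is a separate limb. No rate supports the word largely.
- *That only Arm B is affected.* Continuing 5FU after oxaliplatin neuropathy means that Arm A patients are missed too. Arm B shares that gap and carries the cetuximab condition on top of it.
- *That the bias always makes Arm B look safer, and significantly so.* The direction is fixed only with equal stopping rates and q below 1. Counts of 13 and 3 out of 134 would give a Fisher p of 0.018, but that describes one component under an invented q. With 13 against 7, p is 0.24. If 20 other patients per arm (a further assumption) had a different component, 13 against 3 becomes 33 against 23 on the composite, with p = 0.18.
- *That this is the main safety comparison.* The protocol does not rank it so. It is one of several secondary outcomes, and no secondary aim mentions it.

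**Conclusion.** The point holds in this form. As written, the toxicity item is shut out by the surgery-related proviso in both arms. If the proviso is not applied to it, the item's discontinuation limb is a harder test in Arm B than in Arm A, because section 9.b continues cetuximab when chemotherapy stops for toxicity. The two defects do not act together: the imbalance between arms arises only on the second reading, and the death limb is then neutral.

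On that second reading, the Arm B count of full chemotherapy stops is multiplied by q. With equal stopping rates of 10%, the component would record 13.4 against 1.3 to 6.7 for q from 0.1 to 0.5, and the gap closes at q = 1. Both p and q are assumptions, so these figures show the mechanism and do not forecast the result. They concern one component of a composite secondary outcome. The primary analysis of progression-free survival and the sample size are untouched.

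**What to change.** Reconcile the definition in section 6 with section 9.b by changing the endpoint wording only:

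1. Take the toxicity item out of the list governed by the surgery-related proviso and make it a separate item, counted whatever its relation to surgery.
2. Define its discontinuation limb identically in both arms, as permanent stop of all cytotoxic chemotherapy for toxicity, and keep toxic death as the other limb.
3. Report permanent stop of any study drug for toxicity alongside, drug by drug, so that stops of cetuximab alone are visible.

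No treatment rule changes. The cost is small but not nil. Section 11.e shows that cetuximab administration details are recorded, but it does not say that the reason for permanently stopping each drug is captured, and the form itself is not shown. That has to be confirmed, and the field added if it is absent.
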